3.1 General Design Considerations

The overall adaptive design is a Phase 2b/3 trial, in which dose-ranging with response-adaptive randomization (RAR) (see Appendix 5 for details) is utilized in a first part (the Phase 2b part – Part 1), followed by a traditional 1:1 randomised comparison of selepressin to placebo in the second part (the Phase 3 part – Part 2). The final analysis uses patients from both parts of the trial. The entire trial, combining both parts, represents an adequate and well-controlled comparison of selepressin and placebo.

In Part 1 of the trial, up to four dosing regimens will be investigated.

Arm 1: Starting dose at 1.7 ng/kg/min, and a max. dose of 2.5 ng/kg/min

Arm 2: Starting dose at 2.5 ng/kg/min, and a max. dose of 3.75 ng/kg/min

Arm 3: Starting dose at 3.5 ng/kg/min, and a max. dose of 5.25 ng/kg/min

Arm 4: Starting dose at 5 ng/kg/min, and a max. dose of 7.5 ng/kg/min

Part 1 comprises a minimum of 300 evaluable patients and a maximum of 800 treated patients. During Part 1, patients will be randomised to placebo or selepressin (Arms 1 to 3). Arm 4 will only be opened between 200 evaluable- 600 treated patients and if there is at least a 50% probability that Arm 3 has a higher expected P&VFD than Arm 2 and if data from the lower dosing levels do not suggest any significant safety signals. To minimize the risk of imbalance between treatment arms, randomisation will be stratified based on trial site, the need for mechanical ventilation (Yes/No), norepinephrine/noradrenaline requirement at baseline (< or \ge 30 μ g/min) and creatinine (< or \ge 150 μ mol/L) (See Appendix 7 for details).

Part 1 will begin with a 200-patients treated "burn-in" period during which fixed randomisation across the treatment arms will be used (one-third of the patients randomised to placebo and two-ninths of the patients to each of the selepressin arms [Arms 1 to 3]). The factors described above will be used to stratify the randomisation.

After completion of the burn-in period, Part 1 will utilize response-adaptive randomisation to preferentially place patients into the arms that appear to have the maximum benefit with respect to the primary endpoint. A fixed fraction (one third) of patients will be randomised to placebo throughout Part 1 to ensure contemporaneous control patients are enrolled throughout the trial.

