9.2.1 Primary Variable Analysis

The primary endpoint, P&VFDs, will be analyzed using a van Elteren test, stratified by need for ventilation (Yes/No), time from onset of shock (onset of any vasopressor) to start of treatment (< or \ge 6 hours), and norepinephrine/noradrenaline requirement at baseline (< or \ge 30 μ g/min).

The primary analysis will compare all patients on all selepressin arms from both parts of the trial (pooled together and treated as a single arm) to all patients on the placebo arm from both parts of the trial (see Appendix 7 for a discussion on treatment estimate bias).

The primary analysis will be a test of superiority using a two-sided 5% significance level test.

Treatment effects will be estimated assuming a negative binomial distribution (to allow for possible overdispersion in a Poisson distribution) for the quantity (30 minus P&VFDs) for survivors, and a binomial distribution to model the probability of surviving. Both models adjusted for need for ventilation (Yes/No), time from onset of shock to start of treatment (< or \geq 6 hours), and norepinephrine/noradrenaline requirement at baseline (< or \geq 30 µg/min) (see Appendix 3 for details). For completeness, the proportion of patients dying, and the P&VFDs for survivors will also be presented.

Page 26 of 80

Furthermore, P&VFDs will be tabulated by treatment arm (including pooled active treatment arms), and presented graphically by histograms and cumulative distributions functions.

The success (statistical/clinical significance) of the trial will be based upon the comparison of the analysis above (all patients on all selepressin arms from both parts of the trial (pooled together and treated as a single arm) compared to all patients on the placebo arm from both parts of the trial).

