The number of new organ failures and the number of new organ dysfunctions will be compared between treatment arms using a negative binomial model with age, modified SOFA score and norepinephrine/noradrenaline requirement at baseline ($\mu g/kg/min$) as covariates, and gender and treatment as factors. The estimated treatment difference (to placebo) with a 95% confidence interval will be presented. The 95% confidence interval for the difference in proportions between treatment groups will be constructed using the delta method (see Appendix 4 for details).

Furthermore, incidence of any new organ failure and any new organ dysfunction, and the number of new organ failures and new organ dysfunctions will be tabulated by treatment arm (including pooled active treatment arms).

9.3.1.7 Renal Replacement Therapy (RRT)-free Days up to Day 30 (excluding patients on RRT for chronic renal failure at time of randomisation)

RRT-free Days is defined as for the primary endpoint with free of treatment with any form of renal replacement therapy defined as continuous renal replacement therapy, intermittent hemodialysis or peritoneal dialysis.

RRT-free Days will be analyzed excluding patients on RRT for chronic renal failure at time of randomisation.

RRT-free Days up to Day 30 will be analyzed in a similar manner as the primary endpoint, with the van Elteren test stratified by need for ventilation (Yes/No), time from onset of shock to start of treatment (< or \ge 6 hours), norepinephrine/noradrenaline requirement at baseline (< or \ge 30 μ g/min) and baseline creatinine (< or \ge 150 μ mol/L).

9.3.1.8 Incidence of RRT up to Day 30 (counting patients who die as on RRT and excluding patients on RRT for chronic renal failure at time of randomisation)

RRT is defined as any form of renal replacement therapy defined as continuous renal replacement therapy, intermittent hemodialysis or peritoneal dialysis. In order to ensure that any reduction in incidence of RRT is not caused by an increase in mortality, all patients dying within the 30-day period will be counted as on RRT. For patients withdrawn prior to Day 30, incidence of RRT will be based on the data available up until the time of withdrawal.

Page 34 of 80

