9.3.2 Morbidity/Mortality

9.3.2.1 Intensive Care Unit (ICU)-free Days up to Day 30

ICU -free Days up to Day 30 will be defined and analyzed in a similar manner as the primary endpoint, with the van Elteren test stratified by need for ventilation (Yes/No), time from onset of shock to start of treatment (< or \ge 6 hours), and norepinephrine/noradrenaline requirement at baseline (< or \ge 30 µg/min) and baseline creatinine (< or \ge 150 µmol/L).

A sensitivity analysis will be performed where the definition of time spent in the ICU will include first admission to emergency department, as some patients will be enrolled and have first IMP treatment in the emergency department.

9.3.2.2 ICU Length of Stay up to Day 30

ICU length of stay is defined as the cumulative periods spent in ICU from start of IMP to 30 days after.

For patients withdrawn or dying while still in ICU up to Day 30, the duration will be based on the data available up until the time of withdrawal or death.

ICU length of stay will be analyzed between treatment groups using the permutation test specified in Section 9.3.1.3 stratified by the combination of time from onset of shock to start of treatment (< or \ge 6 hours), baseline creatinine (< or \ge 150 μ mol/L), norepinephrine/noradrenaline requirement at baseline (< or \ge 30 μ g/min) and need for ventilation (Yes/No).

A sensitivity analysis will be performed where the definition of time spent in the ICU will include first admission to emergency department, as some patients will be enrolled and have first IMP treatment in the emergency department.

9.3.2.3 All-cause Mortality (Defined as the Fraction of Patients That Have Died, Regardless of Cause, by the end of Day 30, Day 90, and Day 180)

Mortality will be analysed by a logistic regression model with the individual SOFA scores and age as covariates and treatment arm as factor. The 95% confidence interval for the difference in proportions between treatment groups will be constructed using the delta method as for incidence of RRT (section 9.3.1.8). There will be no imputations for mortality.

Non-inferiority will be claimed if the upper limit of the two-sided 95% CI of the adjusted difference in proportions is less than 30% of the estimated incidence of mortality in the placebo group. Superiority can be claimed (5) if the upper limit is less than 0.

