The adaptive randomisation algorithm creates a vector of probabilities for the four active treatment arms. This is a "global" probability for the arms, meaning it is over all strata. This section describes the balancing of the adaptive randomisation across the different strata to maintain, as well as possible, the balance of the 8 strata within active treatment arms, while achieving the needed adaptive randomisation.

The 8 strata used to balance the randomisation are based on the two-way classification of mechanical ventilation (MV) (Yes/No), Creatinine (Low/High), and norepinephrine/noradrenaline (NA) use (Low/High). We present the method for modifying the global adaptive randomisation probabilities to create different randomisation probabilities for each strata that will honor the goals of the response adaptive randomisation as well as the goal of balancing the strata in the treatment arms.

The outline of the approach at any interim point of the trial is:

- The response adaptive randomisation probabilities are provided from the efficacy analysis. Label these π_1 , π_2 , π_3 , and π_4 , for the four active doses.
- 2 The odds-ratio of a stratum, for each arm, relative to all other arms, is calculated for the *previously* randomised patients.
- Within each stratum the response adaptive randomisations are modified by the odds-ratios from the previous randomisations to create new odds for each arm that are strata specific.
- 4 The probabilities within each strata are normalized and used for randomisation.

The details of the balancing algorithm are presented below and an example data set is presented.

We label the 8 strata as s=1,...,8. For the previous randomisations, let N_{sa} be the number of stratum s randomised to arm a. The marginals of each stratum and/or arm are labeled with a + symbol.

Date: 20 Nov 2017 E-Statistical Analysis Plan-17877; Ver.9.0

Supersedes: Ver. 8.0 Page 76 of 80

The odds-ratio (modified by adding 0.5 to each cell for handling 0 counts) of the previous patients being randomised to arm a, within stratum s is labeled OR_{sa} :

$$OR_{sa} = \frac{\binom{N_{sa}}{(N_{+a} - N_{sa})}}{\binom{(N_{s+} - N_{sa})}{(N_{++} - N_{+a} - N_{s+} + N_{sa})}}.$$

The global odds of randomising to each arm $(\pi_a/1-\pi_a)$ for new patients is modified by the previous odds-ratio of randomisation to create the new randomisation probabilities by stratum for balancing future patients. The modified odds of randomising to arm a, within stratum s is

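### The primary van Elteren test leaves out creatinine, a randomisation factor that the SAP uses in the same test for other endpoints: a free, low-priority improvement

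*SAP*

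**What the plan says.** On randomisation, Section 3.1 states that "randomisation will be stratified based on trial site, the need for mechanical ventilation (Yes/No), norepinephrine/noradrenaline requirement at baseline", and creatinine cut at 150 µmol/L. Appendix 7 repeats this: "The 8 strata used to balance the randomisation are based on the two-way classification of mechanical ventilation (MV) (Yes/No), Creatinine (Low/High"), together with norepinephrine use.

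On the primary test, Section 9.2.1 has a van Elteren test "stratified by need for ventilation (Yes/No), time from onset of shock" to start of treatment (cut at 6 hours), and norepinephrine (cut at 30 µg/min). The survival model and the negative binomial model behind the treatment estimate, detailed in Appendix 3, use the same three factors. On the level: "The primary analysis will be a test of superiority using a two-sided 5% significance level test".

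On other endpoints, Section 9.3.2.1 says "ICU -free Days up to Day 30 will be defined and analyzed in a similar manner as the primary endpoint", but adds creatinine as a fourth factor. Section 9.3.1.7 (RRT-free days) does the same with the words "and baseline creatinine (< or" ≥150 µmol/L), and so does Section 9.4.1 (hospital-free days). RRT-free and ICU-free days are key secondary endpoints in the Hochberg family.

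The SAP gives no reason why the primary endpoint is treated differently.

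**The concern.** The primary test drops a factor used to balance the arms and takes in one (time from shock onset) that was not. The van Elteren null variance is computed from the spread of ranks within the analysis strata. If creatinine predicts the endpoint, part of that spread is between creatinine levels. Stratified allocation has already removed this part from the placebo-versus-active comparison. The computed variance is then larger than the true one, so the test runs a little below its nominal level and loses some precision.

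The SAP itself treats renal status as prognostic. The individual SOFA scores, renal included, adjust the mortality model (Section 9.3.2.3) and are the example covariates of the severity model (Section 9.2.2). Death sets the primary endpoint to zero (Section 9.2). At stake is a small amount of efficiency in the one test that decides success, and consistency between that test and two of the three key secondary analyses.

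**Working it through.** **Inputs from the SAP.** 1800 evaluable patients; effect of 1.5 points lower mortality and 1.5 more days in survivors; stated power 91%, or 98% for the 2-point/2-day case (Section 3.2). Placebo: 25% mortality, 24 days in survivors, 18 overall (Appendix 8). Allocation 1:2 placebo to active in Part 1, at most 800 treated, then 1:1 (Sections 3.1 and 11, Appendix 7).

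**The plan's own figures.** Overall effect = survival × mean days in survivors − 18:
- 0.765 × 25.5 − 18 = 1.51 days
- 0.77 × 26 − 18 = 2.02 days

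Both agree with the stated 1.5 and 2. The 91% cannot be strictly reproduced, because the dispersion among survivors is not given with the power inputs and the figure includes futility stopping. With negative binomial days on support (mean 30 − 24 = 6), 767 placebo and 1033 active patients, and an unstratified Wilcoxon test, dispersion 1.0 gives 94.8% and 1.5 gives 83.1%. A value of about 1.15 to 1.2 would match 91%. The illustrative d = 1/16 in Appendix 3 gives about 100%.

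**Cell counts.** Three binary factors give 8 cells, 1800 / 8 = 225 patients on average. Four give 16 cells, 1800 / 16 = 112.5.

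**Simulation of the two tests.** z = Σ(T − E)/(N + 1) ÷ √[ΣV/(N + 1)²], with tie-corrected V. There were 800 patients at 1:2, then 1000 at 1:1, blocked within ventilation × creatinine × norepinephrine. Assumed prevalences: ventilation 60%, norepinephrine ≥30 µg/min 35%, creatinine ≥150 µmol/L 50%, and 40% in one of the two time-from-onset groups. No futility rule, dose-arm adaptation or site lists were simulated. The creatinine effect is an assumed odds ratio for death and an assumed ratio of days on support.

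| Dispersion | Death OR / days ratio | Null SD, 8 → 16 cells | Two-sided error | Power |
|---|---|---|---|---|
| 1.25 | 1 / 1 | 1.007 → 1.007 | 5.27% → 5.22% | 90.31% → 90.22% |
| 1.25 | 1.5 / 1.15 | 0.987 → 0.992 | 4.64% → 4.77% | 90.35% → 90.42% |
| 1.25 | 2 / 1.3 | 0.984 → 0.999 | 4.72% → 5.02% | 90.25% → 90.55% |
| 1.05 | 3 / 1.5 | 0.964 → 0.996 | 4.00% → 4.70% | 93.83% → 94.56% |

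Rows at dispersion 1.25 use 32,000 null and 24,000 alternative trials; the last row uses 10,000 and 8,000. Monte Carlo error is about 0.1 to 0.2 points for type I error and 0.2 to 0.3 for power, so differences of 0.1 point are noise.

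**Cross-check of the level.** With null SD s, the two-sided error is 2 × [1 − Φ(1.96/s)]. For s = 0.984 it is 2 × [1 − Φ(1.992)] = 4.6%; for s = 0.964 it is 2 × [1 − Φ(2.033)] = 4.2%. Both agree with the simulated 4.72% and 4.00% within Monte Carlo error.

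**Power differences.** −0.09, 0.07, 0.30 and 0.73 points (0.8 from the rounded 93.8% and 94.6%).

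**The case against.** The strongest reply is that this is an endpoint-specific choice. The shock and ventilation endpoints (P&VFDs, vasopressor-free and ventilator-free days, durations of shock and ventilation) omit creatinine. The renal and length-of-stay endpoints include it. That pattern is real, and the protocol, not at hand, may explain it. It means one cannot say that the omission has no reason, only that the SAP states none. It does not show that leaving the factor out is better.

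Other points that stand:
- The prognostic strength and the 50% prevalence are assumptions. The only split in the SAP, the illustrative Table 2 of Appendix 7, has 39 of 140 (28%) in the high-creatinine strata.
- Burn-in and Part 2 use lists by site and stratum. Many incomplete blocks would loosen the creatinine balance and shrink the conservatism. This would not make the addition harmful.
- Some of the 16 cells will be small. The SAP already accepts that for three endpoints.
- The post-simulation bootstrap p-value (Section 9.2.2, Appendix 6) resamples within strata and may correct part of the conservatism, but it is only a sensitivity analysis.

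A reader might infer more than the documents support:
- *That the primary test is invalid or its error rate inflated.* The error moves below nominal, not above.
- *That the 91% is overstated.* Appendix 5 says the operating characteristics were simulated without strata, with a Wilcoxon test.
- *That up to 2 power points are lost.* A run of only 1500 trials at an assumed OR of 2.5 gave 76.7% against 78.3%, at a base power well below the plan's. The larger runs near 90% or above do not reach that.
- *That site should go in as well.* Stratifying by site would give very sparse cells.

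**Conclusion.** The omission and the inconsistency with Sections 9.3.1.7, 9.3.2.1 and 9.4.1 are plain in the text. The consequence is small. Under assumed moderate to strong creatinine effects, the null SD is about 0.96 to 0.98 and about 0 to 0.8 power points are given up. The upper end needs an odds ratio for death of 3 together with 50% more days on support. With no creatinine effect the two tests cannot be told apart. The primary test stays valid and the stated power stands. This is a free improvement of low priority, resting on an assumed prognostic strength and a simplified allocation.

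**What to change.** Before unblinding, add baseline creatinine (< or ≥150 µmol/L) as a fourth stratification factor in the primary van Elteren test, and as a covariate in the survival and negative binomial models of Appendix 3, as Sections 9.3.1.7 and 9.3.2.1 already do for their tests. The final test statistic in the post-simulation bootstrap should follow the primary test, so that observed and simulated statistics are comparable.

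The interim predictive-probability model in Appendix 5 need not change. It is built on eight strata throughout, so sixteen would mean rebuilding the model behind arm selection and futility, which is far more than wording, for a difference of less than one power point.

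The variable is collected for randomisation, so the cost is SAP text and a small programming change. Because the SAP states that its analyses were fixed before the futility stop, a change made after that stop should be dated and labelled as such. The addendum, written after the stop but before unblinding, is the natural place. If the primary test is regarded as locked, the fallback is one sentence of rationale and a pre-specified 16-stratum sensitivity analysis.

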9.2.2 Sensitivity Analyses

The primary analysis will be repeated for the PP analysis set.

As the adaptations of the trial provide a conservative estimate of the p-value, sensitivity p-values will be provided using post-simulation bootstrap calculations (see Appendix 6 for details).

In order to check for consistency the primary endpoint treatment differences will, as a minimum, be estimated and presented by forest plots for the following subgroups

- region (US/Canada vs. Europe)
- age ($<65, 65-74, 75-84, \ge 85$)
- gender
- race/ethnicity

Furthermore, the primary endpoint will be stratified by severity of the patients, with risk of dying as indicator of severity (Figure 3). Mortality (the risk of dying) will be predicted by a logistic regression model, with relevant baseline characteristics as covariates (e.g. the individual SOFA scores and age). The model used to generate the predicted risk (for all patients) will be based on patients in the placebo arm only, as the risk of dying should reflect the severity in the absence of selepressin. Stratified by the risk of dying (intervals of 20% if suitable, based on the mortality rates in the covariate categories in the model), the treatment effect of the primary endpoint will be presented graphically, in order to visually inspect whether the average treatment effect is distributed evenly across the severity of patients.

Page 27 of 80

[figure not shown]

Figure 3: Risk Based Heterogeneity of the Treatment Effect on P&VFDs over the Risk of Dying (an Example)

The impact and robustness of the imputation of missing data will be checked by analysing data in the following ways

- excluding all patients with missing/imputed data
- imputing the 30-day P&VFD status for patients lost to follow up (or otherwise withdrawn from trial) using the observed ratio of P&VFDs at time of lost to follow up (or time of withdrawal), to the same proportion for a 30-day status

For this analysis the 30-day P&VFD status for patients lost to follow up (or otherwise withdrawn from trial) will be imputed so that the 30-day ratio of P&VFDs is equal to the ratio of P&VFDs at time of lost to follow up (or time of withdrawal). E.g. a patient being lost to follow up at Day 15 with 4 P&VFDs (a ratio of 4/15 P&VFDs per days observed) will be imputed to 8 P&VFDs at Day 30 (equivalent ratio 8/30 = 4/15). Patients having zero P&VFDs at time of lost to follow up will be imputed to a value of zero P&VFDs.

• tipping point analysis

The tipping point analysis will compare all possible combinations of 'best case' and 'worst case' scenarios between placebo and selepressin (Figure 4) for patients lost to follow up (or otherwise withdrawn from trial). Best case being an imputation assuming the remaining days off ventilator and vasopressors, and worst case being an imputation of 0 P&VFDs. Let N_p and N_s be the number of patients in the placebo and selepressin arms with missing data. The tipping point analysis will compare all combinations (from 0 to N_p) of X patients on placebo imputed best case and $N_p - X$

Page 28 of 80

imputed worst case, to Y patients on selepressin imputed best case and N_s-Y imputed worst case. I.e all N_p+1 times N_s+1 combinations will be analysed for the primary endpoint. Since the 'best case' is not the same for all patients (depending on when they were last seen off both ventilator and vasopressors) there are multiple outcomes within each combination. For each combination, the average P-value of the multiple outcomes will be plotted in the tipping point analysis. Below is an example of a tipping point analysis of 25 placebo patients vs. 40 selepressin patients with imputed values. The x- and y-axis displays the number of patients with the 'best case' imputed. In the example below the red area displays the non-significant p-values, indicating that one would have to impute almost all placebo patients to a 'best case' and almost all selepressin to a 'worst case' in order to get non-significant p-values, and hence 'proving' the robustness of the imputation method.

[figure not shown]

Figure 4: Tipping Point Analysis of P&VFDs (an Example)

Also, to make sure that the use of vasopressor in each group is not simply being replaced by an increased use of inotropic agents (e.g. dobutamine, milrinone, levosimendan, and amrinone), there will be a sensitivity analysis of the primary endpoint in which the use of inotropic agents will count as vasopressor use.

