		10.4.1 Summary Statistics	
		10.4.2 Data Listings	. 46
	10.5	Episodes of Hypotension	. 46
11	Interin	n analyses	. 47
12	Deviat	ions from protocol analysis	. 48
13	Refere	nces	. 49
14	Tables	, Listings and Figures	. 50
Apper	ndix 1	EQ-5D-5L Quality Adjusted Life Year (QALY)	. 51
Appei		Critical Adverse Events and Classification of Adverse Events Based on Changes in Laboratory Variables	. 52
Appei	ıdix 3	Estimation of Treatment Effects for P&VFDs	. 53
Appei	and Di	Estimation of Treatment Effects for Difference of Proportions in Incidence of RRT, fference in Number of New Organ Failures and Number of New Organ	
	Dysfur	nctions	. 57
Apper	ndix 6	Formal Proof of Type I Error Control	. 69
Appei	ndix 7	Randomisation Plan.	. 74
			. 79

Date: 20 Nov 2017 E-Statistical Analysis Plan-17877; Ver.9.0

Supersedes: Ver. 8.0 Page 10 of 80

1 Introduction

This document describes the planned statistical analyses for selepressin (FE202158) 000133, and is based on protocol dated July 8th 2016 including amendments 1 and 2.

All analyses in the SAP were planned and pre-specified prior to trial termination due to futility.

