2.2.3 Secondary Endpoints

Organ dysfunction

- Vasopressor-free days up to Day 30
- Mechanical ventilator-free days up to Day 30
- Duration of septic shock up to Day 30

Page 13 of 80

- Duration of mechanical ventilation up to Day 30
- Incidence of RRT up to Day 30 (counting patients who die as on RRT and excluding patients on RRT for chronic renal failure at time of randomisation)
- Duration of RRT up to Day 90 (excluding patients on RRT for chronic renal failure at time of randomisation)
- Daily overall and individual organ (cardiovascular, respiratory, renal, hepatic, coagulation) scores using the modified Sequential Organ Failure Assessment (SOFA) scores until ICU discharge
- Incidence of new organ dysfunctions and new organ failures (based on the SOFA score) up to Days 7 and 30

Morbidity/mortality

- ICU length of stay up to Day 30
- All-cause mortality (defined as the fraction of patients that have died, regardless of cause, by the end of Days 30 and 180)

Fluid balance

- Daily and cumulative fluid balance until ICU discharge (for a maximum of 7 days)
- Daily and cumulative urinary output until ICU discharge (for a maximum of 7 days)

Health-related quality of life

• Change in utility, based on EQ-5D-5L, up to Day 180

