- If the trial is not stopped for futility or proceeding to Part 2 and active treatment Arm 4 has not yet been approved for assignment of patients, the decision can be made to open up Arm 4. Arm 4 is only opened between 200 evaluable and 600 treated patients and if there is at least a 50% probability that Arm 3 has a higher expected P&VFD than Arm 2 and if data from the lower dosing levels do not suggest any significant safety signals.
- If Part 1 reaches its maximum of 800 treated patients and no arm has a predictive probability of Part 2 success of more than 25%, the trial stops with an inconclusive result and will be interpreted as a standalone Phase 2b trial.

During Part 2, interim analyses will be conducted regularly (until 1600 patients have been treated) to allow early termination of the trial for futility. This occurs if the predictive probability of an overall significant result is less than 5%. In addition, if the predictive probability of observing a more than 2% higher mortality in the active arms compared to placebo is greater than 90% then the trial will stop for futility.

Date: 20 Nov 2017 E-Statistical Analysis Plan-17877; Ver.9.0 Supersedes: Ver. 8.0

Page 48 of 80

12 Deviations from protocol analysis

See change log.

Date: 20 Nov 2017 E-Statistical Analysis Plan-17877; Ver.9.0 Supersedes: Ver. 8.0

Page 49 of 80

13 References

- The EuroQol Group (1990). EuroQol-a new facility for the measurement of health-related quality of life. *Health Policy* 16(3): 199-208
- 2 EuroQoL Home page: http://www.euroqol.org/home.html
- Mehta, C.R. and Pocock, S.J. (2011) Adaptive increase in sample size when interim results are promising: A practical guide with examples. *Statistics in Medicine*, 30, 3267-3284.
- 4 Hochberg (1988). A sharper Bonferroni procedure for multiple tests of significance. *Biometrika* 75(4):800-802
- 5 EMEA. (2000). Points to consider on switching between superiority and non-inferiority. CPMP/EWP/482/99.

Date: 20 Nov 2017 E-Statistical Analysis Plan-17877; Ver.9.0 Supersedes: Ver. 8.0

Page 50 of 80

14 Tables, Listings and Figures

The document with tables, figures and listings (TLF) shells will be presented in a separate document.

Page 51 of 80

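### Fitting the mortality risk model to placebo patients only tilts the risk-banded P&VFD graph towards apparent harm at low risk and benefit at high risk

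*SAP*

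**What the plan says.** SAP Section 9.2.2 predicts each patient's risk of dying by logistic regression, "with relevant baseline characteristics as covariates (e.g. the individual SOFA scores and age", and adds: "The model used to generate the predicted risk (for all patients) will be based on patients in the placebo arm only". The reason given is that risk should describe severity without selepressin. Patients are then grouped by predicted risk ("intervals of 20% if suitable, based on the mortality rates in the covariate categories in the model") and the P&VFD treatment effect is drawn per band, "in order to visually inspect whether the average treatment effect is distributed evenly across the severity of patients". No cross-validation, shrinkage or external model is mentioned.

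Three other places bear on the size of the problem. Section 2.2.3 lists five organ systems: "individual organ (cardiovascular, respiratory, renal, hepatic, coagulation) scores using the modified Sequential Organ Failure Assessment (SOFA) scores". Section 1 states "All analyses in the SAP were planned and pre-specified prior to trial termination due to futility", and Section 9.1 applies the same plan after a premature stop. In Section 11, Part 2 "interim analyses will be conducted regularly (until 1600 patients have been treated) to allow early termination of the trial for futility".

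**The concern.** The same fitted model is in-sample for one arm and out-of-sample for the other. Chance features of the placebo deaths enter the coefficients, so placebo patients who died drift into higher bands and placebo survivors into lower ones. Selepressin patients do not move in this way. Under Section 9.2 a death within 30 days scores zero P&VFDs, so the drift feeds directly into the plotted outcome. With identical arms, placebo looks too good in the low bands and too bad in the high ones.

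The graph exists to show whether the effect is even across severity, and this rule distorts exactly that pattern. After a futile trial, a picture of harm in milder patients and benefit in sicker ones could be believed. Nothing confirmatory is at stake: the van Elteren test, its type I error and the key secondary tests do not use the score.

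**Working it through.** **1. Inputs from the SAP.** Appendix 8 assumes 25% placebo mortality and 24 P&VFDs in placebo survivors, so the overall mean is 0.75 × 24 = 18.0. The design effect in Section 3.2 (1.5% mortality, 1.5 days in survivors) gives 0.765 × 25.5 − 18.0 = 1.51, which reproduces the stated 1.5 P&VFDs. The SAP gives no figure for bias in the graph.

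**2. Placebo numbers.** Placebo is one third of Part 1 and half of Part 2 (Section 3.1). With a Part 1 of N1 patients and 1800 in total, placebo n = N1/3 + (1800 − N1)/2.
- N1 = 800: 267 + 500 = 767 (selepressin 1033).
- N1 = 300: 100 + 750 = 850 (selepressin 950).
- Total 1600 with N1 = 800: 267 + 400 = 667 (selepressin 933).
- Part 1 maximum alone: 267 (selepressin 533).

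**3. First simulation, no treatment effect** (2000–4000 trials per setting). Assumptions: independent standard-normal covariates with log-odds 0.30 each, about 25% mortality, and survivors' days on support gamma with mean 6. The 13-term model has five organ scores in 3 levels and age in 4 (5 × 2 + 3). The 21-term model has five organ scores in 5 levels plus linear age (5 × 4 + 1). The gradient is the selepressin-minus-placebo difference at ≥40% risk minus that at <20%; its true value is zero.

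| Selepressin/placebo | Terms | Mean gradient, placebo-only fit (days) | Single-trial SD | Trials leaning the false way |
|---|---|---|---|---|
| 1033/767 | 6 linear | +0.59 | 1.74 | 65% |
| 933/667 | 6 linear | +0.66 | 1.84 | – |
| 533/267 | 6 linear | +1.7 | 2.7 | – |
| 533/267 | 10 linear | +2.3 | 2.3 | – |
| 933/667 | 13, categorised | +1.9 | 1.8 | 86% |
| 933/667 | 21, categorised | +2.7 | 1.7 | 94% |

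Chance alone would give 50% in the last column. In the first row the bias is 0.59/1.74 = 0.34 SD (Monte Carlo SE 0.03 days). Its band differences (<20, 20–40, 40–60, ≥60%) are −0.19, +0.02, +0.34 and +0.71 days. A pooled fit of both arms keeps the mean gradient within 0.1 day of zero in every null setting.

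**4. Second simulation, different assumptions** (1500 null trials per setting; negative binomial support days, mean 6, dispersion 1; true c-statistic 0.70). Selepressin-minus-placebo P&VFDs by risk band:

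| Placebo n, terms | Fit | 0–20% | 20–40% | 40–60% | 60–80% |
|---|---|---|---|---|---|
| 850, 6 | placebo only | −0.14 | −0.02 | +0.29 | +0.61 |
| 767, 6 | placebo only | −0.16 | −0.01 | +0.36 | +0.77 |
| 767, 23 | placebo only | −0.68 | +0.06 | +1.38 | +2.64 |
| 267, 6 | placebo only | −0.50 | +0.06 | +0.89 | +2.61 |
| 267, 23 | placebo only | −1.64 | +0.19 | +2.90 | +5.79 |
| 767, 6 | pooled, treatment term, predicted at placebo | 0.00 | −0.02 | −0.01 | +0.03 |
| 267, 23 | pooled, treatment term, predicted at placebo | −0.02 | −0.05 | +0.14 | +0.11 |

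With a c-statistic of 0.79 the pattern is the same but smaller: at 850 placebo patients and 6 terms, −0.08, −0.02, +0.20 and +0.33.

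**5. Mechanism.** At 267 placebo patients and 23 terms, placebo/selepressin mortality is 10/17% in the lowest band and 69/45% in the 60–80% band, although true risks are identical. At 24 P&VFDs per survivor this implies (0.10 − 0.17) × 24 = −1.7 and (0.69 − 0.45) × 24 = +5.8 days. These match −1.64 and +5.79, so the false effect comes from how deaths are sorted into bands.

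**6. Under the planned effect** (first simulation, 1033/767, 6 linear terms; log-odds of death −0.0824 and support days × 0.75 on selepressin). Banding on true risk gives a mean gradient of −0.27 days, the pooled fit −0.31 and the placebo-only fit +0.33.

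**The case against.** The mechanism and its direction are not in dispute; the weight is.

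- **Number of terms.** Section 9.3.2.3 uses individual SOFA scores and age as covariates, and the SAP elsewhere keeps covariates apart from factors. Six linear terms is therefore the natural reading. The wording "based on the mortality rates in the covariate categories in the model" qualifies the band width, not the coding. This has force: the 13-, 21- and 23-term models are possibilities, not the plan. But the SAP gives its covariates only as examples, so it does not secure the small case.
- **Noise.** With six terms at 1600–1800 patients the bias is about a third of a single-trial SD. Stronger covariates (log-odds 0.45 each) reduce it to +0.42 days (SD 1.45) at 1033/767. This stands, and the base case is modest.
- **Sign.** Under the planned effect, banding on true risk itself gives a positive gradient in 46% of trials, against 62% for the placebo-only fit. One graph could not settle the sign. This also stands: the reversal concerns the average, not any single trial.
- **Sample size.** The SAP does not say how many patients had been treated at the futility stop, so the Part 1-sized arm is an assumption.
- **Consequence.** No test or decision rests on this graph. Forest plots of fixed subgroups and the addendum's graphs by baseline norepinephrine do not use the fitted score. True, but they do not correct this graph.
- **Rationale.** The placebo-only fit has a stated purpose, risk without selepressin. A pooled fit can serve it too, as shown under the fix.

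**Conclusion.** The concern holds. The placebo-only fit introduces a systematic tilt, in the same direction in every setting tried: harm in the lowest band, about nothing at 20–40% risk, benefit above 40%. With six linear terms at full enrolment it is small, about +0.6 days between high and low risk. With a Part 1-sized placebo arm or many categorised terms it matches or exceeds the whole 1.5-day design effect.

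The direction follows from the written rule. The size rests on assumptions outside the SAP: number and coding of terms, discrimination, placebo numbers at the stop, independent covariates, and survivors' P&VFDs unrelated to risk. The damage is confined to one descriptive graph. The change is worth making because it is cheap and removes a bias in the one feature the graph is meant to show; it is not a threat to the trial's conclusions.

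**What to change.** Replace the sentence in Section 9.2.2 with one stating that the mortality model is fitted to all patients, both arms pooled and without a treatment term, and that this score defines the bands. List the covariates and their coding.

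The cost is one sentence and a few lines of code, with no new data. The addendum places itself before unblinding and carries the same date as SAP version 9.0, so at that date the change could be made without sight of results. The downside is that the score reflects average rather than untreated risk. This matters little for planned mortality differences of 1.5–2%: under the planned effect the pooled fit came within 0.04 days of banding on true risk (−0.31 against −0.27). To keep the stated aim, a pooled model with a treatment term, predicted at placebo for everyone, also removes nearly all the bias.

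Ordinary ten-fold left-out predictions for placebo patients are not equivalent. They shrink the bias but reverse it: −0.34 days at 1033/767 and −0.82 at 533/267 with six linear terms, against +0.59 and +1.7.
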